1.0 STUDY SUMMARY

| | |
|--|---|
| Name of Sponsor: Sunstar Americas, Inc. | Device: [REDACTED] Growth Factor Enhanced Bone Graft Substitute |
| Title of Protocol: A Randomized, Double-Blind, Controlled, Multicenter Dose Verification Clinical Trial to Evaluate the Safety and Effectiveness of [REDACTED] Growth Factor Enhanced Bone Graft Substitute for the Treatment of Periodontal Defects 6-months Post-Surgery | IDE No.: Pending |
| Study Number: CLP- 2011-10-31-1 | Study Start: After IDE and site IRB approval |
| Enrollment Completion Planned: TBD | |
| Study Design: This will be a prospective, randomized, double-blinded, controlled, multi-center, dose-verification clinical study in subjects who require surgical intervention to treat a qualifying periodontal defect. Treatment randomization will be stratified by smoking status. The parallel arms will be: Treatment I: β -TCP alone (active control) Treatment II: [REDACTED] GFeBGS: consisting of β -TCP and 0.1% rh-bFGF Treatment III: [REDACTED] GFeBGS: consisting of β -TCP and 0.3% rh-bFGF Treatment IV: [REDACTED] GFeBGS: consisting of β -TCP and 0.4% rh-bFGF After signing an informed consent for screening, being screened, having pre-surgical treatment and baseline measurements, signing an informed consent for study enrollment, subjects meeting inclusion criteria and not meeting any exclusion criteria will be randomized to one of four groups so that treatment is balanced within each investigational site and according to smoking status. Enrollment will be defined as randomization to one of the above-mentioned study arms. Investigators who perform evaluations will remain blinded to the investigational device implantation of all subjects for the 6-months post-surgery. The roles of Investigator will be determined at the start of the study and will remain until completion of the study. The study will be conducted in accordance with the Declaration of Helsinki (1996) and Good Clinical Practices (GCPs). The study will receive IRB approval at each investigational site prior to commencement of the study. Investigators will administer treatments to subjects following pre-surgical procedures, and subjects will receive surgical implantation of the investigational device or the active control in the intrabony periodontal defect located at the target tooth having pocket depths (PD) \geq 7 mm and vertical bone defect \geq 4 mm with at least 1 defect wall. Wound-healing (WH) scale of the surgical site will be examined at 2 and 4 weeks post-surgery. Clinical examinations, clinical attachment level (CAL), probing depth (PD), gingival recession (GR) and bleeding on probing (BOP), of the treated tooth will be performed at 3 and 6 months. Radiographic examination will also be performed at baseline, 3 and 6 months. After all subjects complete the 6-month follow-up post-surgery, the data will be assessed to select the optimal therapeutic rh-bFGF dose. Primary Objective: To obtain dosing data on [REDACTED] Growth Factor enhanced Bone Graft Substitute (GFeBGS) for the | |

treatment of periodontal intrabony defects and to help guide the selection of dosing for future study.

Subject Population: Subjects 25 years and older with advanced periodontal disease in at least one site requiring surgical treatment to correct a bone defect. A total of 94 subjects will be randomized to obtain a minimum of 80 evaluable subjects for this multicenter trial.

| Number of Subjects: | Number of investigational sites: |
|-----------------------|----------------------------------|
| 80 evaluable subjects | 6 sites |

Main Criteria for Inclusion:

Inclusion criteria include:

1. Male or female, age of 25 and older
2. Must have read, understood, and signed a consent form
3. Must be able and willing to follow study procedures and instructions
4. Must have undergone thorough scaling and root planing of the test site and be expected to demonstrate good plaque control after instruction in oral hygiene
5. The treated site must exhibit the following:
 - A pocket depth of 7 mm or greater
 - After surgical debridement, 4 mm or greater intrabony defect with at least 1 bony wall
 - Sufficient keratinized tissue to allow complete tissue coverage of the defect
 - Radiographic base of defect at least 3 mm coronal to the apex of the tooth

Main Criteria for Exclusion:

Significant exclusionary criteria are:

1. Failure to maintain adequate oral hygiene during the screening phase
2. Women of child-bearing potential
3. A history within the last 6 months of HIV, Type IV heart disease, or end-stage renal disease
4. A history of oral cancer or any other cancer (except for end of treatment for skin cancers such as squamous and basal carcinoma with end of treatment at least 6 months ago and/or prostate cancer with end of treatment at least 5 years ago)
5. A history within 12 months of previous open flap periodontal surgery on the study tooth
6. A diagnosis of pre-malignant oral lesion(s)
7. A traumatic occlusion of the target tooth
8. Target "study" tooth exhibiting Grade III mobility
9. Maxillary molars or maxillary first premolar with a prominent mesial concavity
10. Study tooth exhibiting a Class II or greater furcation defect
11. Clinical or radiographic signs of untreated acute or chronic periapical infection at the surgical site, apical pathology, root fracture, severe root irregularities, cemental pearls, cervical enamel projections not easily removed by odontoplasty, untreated carious lesions at the cemento-enamel junction (CEJ) or on the root surface, or restorations with open or otherwise defective margins at or below the CEJ
12. A history within the last 6 months of the daily use of any tobacco products besides cigarettes (smokeless chewing tobacco, pipe or cigar smoking), or of smoking more than 10 cigarettes per day
13. Subjects participating in other clinical trials within 30 days of enrollment
14. Subjects having uncontrolled endocrine-induced diseases (e.g. uncontrolled diabetes mellitus and

hyperparathyroidism)

15. Subjects undergoing current therapy with systemic steroids or other drugs that significantly alter bone metabolism
16. Subjects with Localized, Juvenile Periodontitis (LJP) sites in the oral cavity

Investigational Device Administration:

The investigational device, [REDACTED] GFeBGS as a “kit” product, consists of the synthetic bone graft substitute (β -TCP) granule saturated with reconstituted recombinant human basic fibroblast growth factor (rh-bFGF). The β -TCP is supplied in a sterile particulate form in one container. The active device kits contain a vial with a sterile lyophilized cake that contains rh-bFGF. The active control device kits contain a vial with a sterile lyophilized cake that does not contain rh-bFGF. The kits also contain a solvent, 1% hydroxypropyl cellulose (HPC) solution supplied in a sterile prefilled syringe for reconstituting lyophilized cake. The β -TCP is saturated with the reconstituted solution during the periodontal surgical procedures and placed into the periodontal defect.

Main Criteria for Evaluation and Analyses:

The primary effectiveness endpoint is a composite endpoint that considers radiographic and clinical measurements at six months post-implantation: the amount of linear bone growth (LBG), which is assessed with the use of radiographs, and the regain from baseline of clinical attachment level (Δ CAL), which is calculated from clinical assessments. The success criteria are a minimum of 1.5 mm for Δ CAL and a minimum of 1 mm for LBG. Both the Δ CAL and LBG must meet the success criteria for a subject to be considered a success.

The secondary endpoints will include the mean Δ CAL from baseline at three and six months and the mean Δ CAL between study treatments at three and six months post-implantation; the LBG at six months; percent bone fill (%BF) in a vertical and horizontal direction compared to baseline and six months post-implantation, a composite endpoint combining Δ CAL and %BF; Probing Depth Reduction (PDR) from baseline at three and six months post-implantation, Change in Gingival Recession (Δ GR) from baseline at three and six months post-implantation; Wound-Healing (WH) scale and gingival wound evaluation during the first four weeks, and bleeding on probing (BOP) at three months.

Dose Selection Overview:

The goal of the feasibility study is to identify either the 0.1%, 0.3% or 0.4% active dose to be compared vs. the β -TCP control in a pivotal study, based on the observed safety and effectiveness together with past study results. No formal interim analyses are planned.

This study will not be used for labeling purposes, but will be used to plan the subsequent pivotal study. The Sponsor retains the right to pick any of the three active doses moving forward to the pivotal study.

Statistical Considerations:

The primary effectiveness endpoint is a composite endpoint that considers radiographic and clinical measurements at six months post-implantation: the amount of linear bone growth (LBG), which is assessed with the use of radiographs, and the change from baseline of clinical attachment level (Δ CAL), which is calculated from clinical assessments. To be a success, Δ CAL ($CAL_{6\text{ mo}} - CAL_{\text{Baseline}}$) must be at least -1.5 mm and a minimum measurement of 1 mm is required for linear bone growth (LBG) measured from baseline; both must be met at 6 months to define a primary effectiveness success for the tooth (Lynch S, Lavin P *et al. J Periodontal* 2006;77:1314). The number of teeth that meet the success criteria for the primary endpoint will be compared between the study treatments. The components of the primary effectiveness outcome, including LBG in particular, are also of interest.

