5.2.2 Primary Effectiveness Endpoint

The primary effectiveness endpoint is a composite endpoint that considers radiographic and clinical measurements at six months post-implantation: the amount of linear bone growth (LBG), which is assessed with the use of radiographs, and the regain from baseline of clinical attachment level (Δ CAL), which is assessed clinically. LBG is a representative measurement of alveolar bone re-growth that is measured in a vertical and horizontal direction using radiographs. The clinical attachment level (CAL) is the distance from the cemento-enamel junction (CEJ) (or other fixed

reference point) generally along the long axis of the tooth to the deepest extent of the periodontal pocket. CAL is the established clinical parameter to be used for evaluation of connective tissue regeneration and 1.5 mm is the historically established level of clinical efficacy for guided tissue regeneration (GTR) products that attempt to regenerate periodontal structures. The success criteria are a minimum of 1.5 mm for Δ CAL and a minimum of 1 mm for LBG. Both the Δ CAL and LBG must meet the success criteria for a subject to be considered a success.

LBG was selected as a component of the primary endpoint because it was shown to be the most sensitive measurement of alveolar bone re-growth in a recent trial for a different bone graft substitution used in a similar indication⁽⁶⁾. The soft tissue and bone components are each important to a clinically successful outcome and periodontitis, which by definition affects both the connective tissue like periodontal ligament and alveolar bone, is an established fact. Furthermore, in Sunstar dog studies, it was also demonstrated that β -TCP itself achieved a good bone regeneration but not cementum. Rh-bFGF must contribute to not only bone regeneration but also new cementum and matured periodontal ligament regenerations. Therefore, to determine whether this product achieves the regeneration of all periodontal tissues, the composite endpoint combining clinical parameter (Δ CAL) with radiographic parameter (LBG) was selected as the primary endpoint.

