8.1.2 Clinical Outcomes

The Investigator and other qualified site personnel (i.e. Dentist, Dental Hygienist) will perform the clinical examinations using the following methods at the examination visits. Clinical Measurement will be performed throughout pre-treatment, baseline and post-treatment follow-up visits during the trial. Intra-Surgical Measurement will be performed at Visit 5 only.

Only calibrated North Carolina 15 mm periodontal probes will be used. The measurements will be rounded off to the nearest millimeter (0.5 mm is to be rounded up). Clinical probing measurements will be made at the mid-facial, mesial and distal line angles and at mid-lingual, mesial, distal line angles with a calibrated probe. The measurements will be made at these standard locations to the deepest part of the defect.

Clinical Measurement

- Pocket depth (PD): From free gingival margin to the base of the pocket
- Clinical attachment level (CAL): will be calculated by adding PD and GR.
- Gingival recession (GR): From the free gingival margin to the CEJ

Intra-Surgical Measurement (Visit 5 only)

- Alveolar crest height (ACH): From cemento-enamel junction to alveolar crest (CEJ-AC)
- Base of defect from CEJ (BD): From cemento-enamel junction to the base of osseous defect (CEJ-BD)
- Vertical bone defect depth at its deepest location (vBD): vBD will be calculated by subtracting ACH from BD

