12.1 Statistical and Analytical Plans

Primary Effectiveness Endpoints:

The primary effectiveness outcome in this trial is the radiographic and clinical composite which is a combination of an amount of linear bone growth (LBG) and change of clinical attachment level (CAL) clinically measured from baseline at the six month post-implantation. The thresholds to be used are 1.5 mm for Δ CAL and 1 mm for LBG.

Secondary Effectiveness Endpoints:

There are nine secondary effectiveness outcomes which are described in Section 5.2.3.

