12.1.1 Hypothesis Testing

As this is a feasibility study, formal hypothesis tests for the purposes of regulatory approval or labeling claims will not be performed. Nonetheless, for internal purposes, statistical hypothesis tests may be performed as follows.

A two-sided superiority hypothesis test follows for the composite success percent endpoint:

$$\begin{aligned} H_0: p_G - p_C &= 0, \text{ versus} \\ H_a: p_G - p_C &\neq 0 \end{aligned}$$

where p_G and p_C are the respective percents of subjects achieving success as specified above for [REDACTED] GFeBGS and Active control treatment groups. This hypothesis testing format will be used for the other effectiveness endpoints measured as success outcomes.

The two-sided superiority hypothesis test is the following for the continuous and percent based measures relative to baseline:

$$\begin{aligned} H_0: \Delta_G - \Delta_C &= 0, \text{ versus} \\ H_a: \Delta_G - \Delta_C &\neq 0 \end{aligned}$$

where Δ_G and Δ_C are the respective mean changes in outcomes relative to baseline for [REDACTED] GFeBGS and Active control treatment groups. The same hypothesis testing format will be used for other continuous effectiveness endpoints.

For each primary and secondary effectiveness endpoint, an alpha level of 0.05 will be used.

CONFIDENTIAL

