12.1.9 Secondary Effectiveness Analysis

Superiority will be tested for the continuous effectiveness endpoints (e.g. Δ CAL, LBG, %BF, PD) using an ANCOVA model with the same baseline covariates as specified above and in addition, the corresponding baseline value for each endpoint. The ANCOVA model will include the same covariates as for the primary effectiveness endpoint. The two-sided 95% lower bound for the LSMEAN difference between each of the three GFeBGS treatment groups minus Active control will need to exceed 0 to achieve superiority.

Additional ANCOVA models will also evaluate any additional covariates found to be imbalanced ($p \leq 0.05$) at baseline.

Effectiveness outcomes will be displayed at every visit in order to characterize the time of onset and duration of effectiveness throughout the study. Results will be displayed for subjects who complete the study as planned as well as for those withdrawn early; the patterns of withdrawal will be displayed for each study treatment group to assess if reasons withdrawn were different in any respect.

Analyses will also be conducted for the other effectiveness endpoints inclusive of PDR, GR, WH, and BOP; the second composite endpoint (Δ CAL, %BF) will be analyzed in the same manner as for the first composite endpoint. In general, for continuous variables, the mean, median, standard deviation, minimum and maximum values will be displayed; for ordinal and categorical variables,

CONFIDENTIAL

frequencies and percentages will be displayed. When relevant, the mean changes from pre-operative baseline will be computed for all treatment groups at each visit through study exit; an unpaired t-test will be used to test for improvement between the treatment groups while a paired t-test will be used to test for improvement within the treatment groups. Superiority will be tested for continuous outcomes using an unpaired t-test by examining the two-sided 95% lower bound for the difference between GFeBGS minus Active control to test if the lower bound exceeds 0. The percents achieving predefined effectiveness milestones will be displayed at each post-baseline time through each stage; a two-sided Fisher Exact test will be used to test for superiority.

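### The summary's CAL success criterion for the primary composite has its inequality reversed: on six-month minus baseline it passes attachment loss and fails every regain above 1.5 mm

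*Protocol*

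**What the plan says.** The CAL half of the primary composite is described in several places.

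- **Section 1.0, Main Criteria for Evaluation and Analyses**, calls the measure "the regain from baseline of clinical attachment level" and sets the success threshold at a minimum of 1.5 mm. Section 4.2.1 also calls it a regain.
- **Section 5.2.2** does the same: "The success criteria are a minimum of 1.5 mm for" the CAL measure, with 1 mm for LBG, both to be met.
- **Section 1.0, Statistical Considerations**, calls it a change, writes it as CAL at six months minus CAL at baseline, and says it "must be at least -1.5 mm and a minimum measurement of 1 mm is required for linear bone growth (LBG) measured from baseline". No other place in the protocol gives a subtraction order for CAL.
- **Section 12.1** again calls it a change and gives no sign or direction: "The thresholds to be used are 1.5 mm for" CAL and 1 mm for LBG.
- **Section 8.1.2** fixes the scale: CAL "will be calculated by adding PD and GR", with probing readings rounded to whole millimetres.

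For continuous endpoints, section 12.1.1 compares quantities that "are the respective mean changes in outcomes relative to baseline for" the two groups. Section 12.1.9 gives examples of the endpoints, starting with CAL change and continuing "LBG, %BF, PD) using an ANCOVA model with the same baseline covariates as specified above". It then claims superiority when the lower confidence bound for GFeBGS minus control is above 0.

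**The concern.** The Statistical Considerations paragraph takes a measure on which improvement is negative and requires it to be no lower than -1.5 mm. The minus sign suits the subtraction order; the direction of the inequality does not. As written, the sentence is very nearly the complement of the rule in Main Criteria and in section 5.2.2.

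This is a stated decision threshold, not a detail left for later. CAL is one of the two components of the primary composite, and section 12.1.10 bases dose selection on that composite. Anyone who needs an explicit formula finds only the one in the summary.

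The same question of sign touches section 12.1.9. One rule, lower bound above 0, is applied to a list that includes CAL change and PD, and neither has its favourable direction stated there.

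**Working it through.** **Inputs.** CAL = PD + GR, in whole millimetres (section 8.1.2). Change d = CAL at six months minus CAL at baseline (section 1.0, Statistical Considerations). Threshold 1.5 mm (sections 1.0, 5.2.2 and 12.1).

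**The plan's own power figure.** Section 12.1.2 states at least 80% power with 20 subjects per group, for an LBG difference of 1.70 mm with SDs of 1.20 and 2.30 mm. An unequal-variance t-test at two-sided 5% gives 80.8%, so the figure reproduces. CAL does not enter it, and nothing below changes it.

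**The two CAL rules.**

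- Regain rule (Main Criteria and section 5.2.2): regain = -d, pass if -d >= 1.5, that is d <= -1.5.
- Literal rule (Statistical Considerations): pass if d >= -1.5.

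**Single site, whole millimetres, d from -4 to +3 (8 values).**

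| d (mm) | Meaning | Regain rule | Literal rule |
|---|---|---|---|
| -4 | regain of 4 | pass | fail |
| -3 | regain of 3 | pass | fail |
| -2 | regain of 2 | pass | fail |
| -1 | regain of 1 | fail | pass |
| 0 | no change | fail | pass |
| +1 | loss of 1 | fail | pass |
| +2 | loss of 2 | fail | pass |
| +3 | loss of 3 | fail | pass |

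The regain rule passes 3 values and the literal rule passes the other 5. All 8 are classified oppositely. The rules agree only at d = -1.5 exactly, which whole-millimetre readings at one site cannot give.

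**If the six probing sites were averaged** (an assumption made only to test sensitivity), d moves in steps of 1/6 mm. From -24/6 to +18/6 there are 43 values. The regain rule passes -24/6 to -9/6, which is 16 values. The literal rule passes -9/6 to +18/6, which is 28 values. Since 16 + 28 = 44, one value (d = -1.5) passes both, none fails both, and 42 of 43 are classified oppositely.

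**Check of the repair.** On six months minus baseline, d <= -1.5 agrees with regain >= 1.5 at each regain tested: -2, -1, 0, 1, 1.5, 2, 3 and 4 mm.

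**Direction in section 12.1.9.** The rule is lower bound of GFeBGS minus control above 0.

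| Measure | Better when | Rule |
|---|---|---|
| LBG (baseline minus follow-up distance, section 8.1.3.3) | higher | right |
| %BF (same numerator as LBG) | higher | right |
| CAL as regain | higher | right |
| CAL as six months minus baseline | lower | reversed |
| PDR as baseline minus follow-up | higher | right |
| Raw PD | lower | reversed |

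For CAL and PD, then, the rule is right or wrong according to a coding that section 12.1.9 does not state.

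**The case against.** The strongest reply is that this is a slip with one sensible reading. The minus sign shows the author knew that improvement is negative on that formula, so the phrase was meant as a magnitude. The paragraphs around it speak of a regain, and section 5.2.3 repeats a positive 1.5 mm minimum for the second composite. Programming would normally follow the statistical analysis plan rather than a synopsis. All of this stands as evidence of intent, and it limits the consequence. It does not make the sentence right: it is the only one with a formula, it concerns the primary endpoint, and it contradicts the same summary.

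It can also be said that counts such as 8 of 8 merely restate what reversing an inequality does, over a range chosen for illustration. That is fair. They describe the CAL rule and do not forecast trial results.

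A reader might go further and infer that section 12.1.9 is itself in error for CAL and PD. The document does not support that. Section 12.1.9 cites no formula, and if CAL is taken as regain its rule is correct; the reversal appears only if the summary's formula is carried forward. PD stands in a list of examples, while the defined secondary endpoint is PDR. The section also describes its t-tests as tests for improvement, and the hypotheses in section 12.1.1 are two-sided and carry no wrong sign. On the other side, the section names PDR separately later on, so PD is not plainly shorthand for it. What remains is an ambiguity worth closing, not a second established error.

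**Conclusion.** Wrong as written. The CAL criterion in Statistical Considerations has its inequality reversed and contradicts Main Criteria and section 5.2.2. Applied literally, it misclassifies the CAL component at every value except a change of exactly -1.5 mm. This follows from the stated formula and from CAL being PD plus GR. The whole-millimetre count rests on the rounding rule in section 8.1.2, and the six-site count on an averaging step that is assumed here.

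The practical reach is limited. A reader might infer that subjects with attachment loss would be counted as composite successes outright, but LBG of at least 1 mm must still be met. Section 12.1 is not wrong in giving an unsigned 1.5 mm; it simply does not resolve the conflict. The tests are for internal use (section 12.1.1), the sponsor may take any of the three doses forward (section 1.0), and the sample size is unaffected. The section 12.1.9 point is conditional on coding and is secondary.

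It should be corrected before any derivation is programmed, because dose selection rests on the composite.

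**What to change.** 1. In section 1.0, Statistical Considerations, define CAL gain as baseline CAL minus six-month CAL, with success if the gain is at least 1.5 mm. Equivalently, keep six months minus baseline and require the change to be -1.5 mm or lower.
2. Use the same signed definition in section 12.1, so that the statistical section stands on its own.
3. In section 12.1.9, write PDR (baseline minus follow-up) in place of PD, and add one sentence saying that endpoints are coded so that a positive value means improvement.

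The cost is a few sentences of wording. The intended endpoint, the sample size and the data collected do not change.
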